6.4 Changes from Protocol-Specified Statistical Analyses

The protocol specifies ITT population as all randomized subjects. This SAP clarifies that ITT population will include all randomized subjects who received study drug. ITT population will exclude subjects who were randomized and did not receive study drug.

There are no significant changes from protocol-specified statistical analysis apart from specifying the type of analysis to be used and further defining endpoints. The SAP will be considered as the governing document and in case of any differences between this SAP and the study protocol, the SAP will supersede the protocol.

6.5 Programming Specifications

Analyses will be performed using SAS® version 9.4 or higher. All available data will be presented in subject data listings which will be sorted by subject and visit date as applicable. Detailed Programming Specifications will be provided in a separate document.

APPENDIX A: CLINICAL LABORATORY TESTS

The tests detailed here will be performed as per local hospital laboratory.

Table 9: Protocol-Required Safety Assessments

| Laboratory Tests | Parameters |
|-------------------|--|
| Hematology | Platelet count (K/mm ³) Hemoglobin (g/dL) Hematocrit (%) |
| Chemistry | Blood Urea Nitrogen (mg/dL) Coagulation Panel (PTT and INR) Liver function test (LFT) panel ((ALT (U/L), AST (U/L) and Bilirubin (mg/dL)) Serum creatinine (mg/dL) Serum glucose (mg/dL) |
| Electrolytes | Sodium (mmol/L) Potassium (mmol/L) Chloride (mmol/L) Bicarbonate (mmol/L) Magnesium (mg/dL) |
| Pregnancy testing | Highly sensitive (serum or urine) human chorionic gonadotropin (β -hCG) pregnancy test (as needed for women of childbearing potential) |

APPENDIX C: DEFINITION OF SAE

| An SAE is defined as any untoward medical occurrence that, at any dose: | |
|--|--|
| a. Results in death | All deaths occurring during the follow up to Day 90 will be reported as an SAE. When reporting a death, the event or condition that caused or contributed to the fatal outcome should be reported as a single medical concept. |
| b. Is life-threatening | The term 'life-threatening' in the definition of 'serious' refers to an event in which the participant was at risk of death at the time of the event. It does not refer to an event, which hypothetically might have caused death, if it were more severe. |
| c. Requires inpatient hospitalization or prolongation of existing hospitalization | 
In general, hospitalization signifies that the participant has been detained (usually involving at least an overnight stay) at the hospital or emergency ward for observation and/or treatment that would not have been appropriate in the physician's office or outpatient setting. Complications that occur during hospitalization are AEs. If a complication prolongs hospitalization or fulfills any other serious criteria, the event is serious. When in doubt as to whether "hospitalization" occurred or was necessary, the AE should be considered serious.Hospitalization for elective treatment of a pre-existing condition that did not worsen from baseline is not considered an AE. |
| d. Results in persistent disability/incapacity | 
The term disability means a substantial disruption of a person's ability to conduct normal life functions.This definition is not intended to include experiences of relatively minor medical significance such as uncomplicated headache, nausea, vomiting, diarrhea, influenza, and accidental trauma (e.g., sprained ankle) which may interfere with or prevent everyday life functions but do not constitute a substantial disruption. |
| e. Results in a congenital anomaly/birth defect | |
| f. Other situations: a SAE can also be an important medical event that may not result in death, be life-threatening, or require hospitalization, but may jeopardize the participant and may require medical or surgical intervention to prevent one of the outcomes listed in this definition: | 
Medical or scientific judgment should be exercised in deciding whether SAE reporting is appropriate in other situations such as important medical events that may not be immediately life-threatening or result in death or hospitalization but may jeopardize the participant or may require medical or surgical intervention to prevent one of the other outcomes listed in the above definition. These events should usually be considered serious. |

- Examples of such events include invasive or malignant cancers, intensive treatment in an emergency room or at home for allergic bronchospasm, blood dyscrasias or convulsions that do not result in hospitalization, or development of drug dependency or drug abuse.

APPENDIX D: POTENTIAL BIOMARKER ANALYSES

Exploratory analyses of biomarkers may be conducted in that subset of the ITT population consisting of subjects who consented to the collection of blood samples for RNA and other biomarkers. A list of the biomarker endpoints to be analyzed may be provided in the future.

Descriptive statistics for each endpoint may be tabulated by treatment arm and time (Day 1, Day 2 and Day 90).

Other possible analyses are as follows:

- To compare qualitatively those subjects who consented to biomarker collection versus the rest of the ITT population, descriptive statistics for important baseline characteristics (to be determined in the future) may be tabulated by subject cohort (those who consented to biomarker collection versus those who did not).
- The relationship between biomarkers and key clinical outcomes (mRS, NIHSS, BI and EQ-5D-5L) may be examined descriptively, as follows:
 - Within each treatment arm and for all treatment arms combined, scatterplots may be generated for each biomarker at Day 90 (horizontal axis) and each clinical outcome at Day 90 (mRS (scale 0-6, not dichotomized, NIHSS, BI, EQ-5D-5L; vertical axis). These may be presented individually or as one or more scatterplot matrices.
 - The Spearman rank correlation coefficients between each biomarker and each clinical outcome may be presented, either superimposed on the corresponding scatterplots as defined above, or tabulated in a separate table.
 - Irrespective of treatment, the empirical probability distribution function (ePDF) of each biomarker at Day 90 may be displayed graphically, one curve for each mutually exclusive subset of subjects as defined by the following cut points of the clinical outcomes at Day 90. For each biomarker, the ePDF curves would be overlaid on the same set of axes. (See Figure 9 of FDA (2018).) The ePDFs may be generated using the SAS UNIVARIATE procedure with the default KERNEL option.
 - a. mRS: 0-2 (No disability), 3-6 (Disability). Thus, two curves may be overlaid—one for subjects with Day 90 mRS in the range 0-2 and the other for subjects with Day 90 mRS in the range 3-6.
 - b. NIHSS: ≤ 5 (Mild), 6-13 (Adequate), ≥ 14 (Severe). Three curves may be overlaid.
 - c. BI: The tertiles of the Day 90 total EQ-5D-5L score would be determined. The biomarker ePDF would be generated for the subjects in each tertile. Three curves may be overlaid.
 - d. EQ-5D-5L: The tertiles of the Day 90 total EQ-5D-5L score would be determined. The biomarker ePDF will be generated for the subjects in each tertile. Three curves may be overlaid.

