3.1.7 Handling of Death

Subjects who die during the study will be scored as follows for all scheduled visits following the death: 6 for mRS, 42 for NIHSS and 0 for BI. The value 6 for mRS is part of the mRS definition. The values for NIHSS and BI are conventions, consistent with the worst possible score.

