The effect of treatment on functional independence at Day 90 will be examined by comparing subjects achieving functional independence (Barthel Index score ≥ 95 as compared to < 95) where subjects having a score ≥ 95 on the Barthel Index Score at Day 90 will be deemed to have achieved functional independence, and those scoring < 95 at Day 90 will be deemed to have failed to achieve functional independence.

The proportion of subjects who achieved functional independence (BI score ≥ 95 vs. < 95) at Day 90 will be compared between the three treatments (RNS60 1.0 mL/kg/h, RNS60 0.5 mL/kg/h, and placebo 1.0 mL/kg/h) using generalized linear mixed modeling using RSPL assuming a binary outcome ($< 95 = 0$, $\geq 95 = 1$). Covariates include the Age, baseline NIHSS, and ASPECTS binary factors used for block urn randomization and baseline BI total, log of baseline infarct volume, baseline perfusion status, baseline occlusion location, and study site. Treatment, visit day, and interaction of treatment and visit day are included as categorical fixed effects.

Sensitivity analysis of BI will be performed in a similar way to the primary analysis using the GLM approach with RSPL assuming a binary outcome ($<95=0$, $\geq 95=1$) where any missing value of BI will be imputed as functional independence not achieved (coded as 0).

3.4.3 Sensitivity Analysis for Secondary Efficacy Endpoints with Dichotomous Data for Baseline Collaterals

For each of the secondary efficacy endpoints described in section 3.4.2, additional sensitivity analysis will be performed using the GLM analysis approach where baseline collaterals will also be included in the model. For subjects with a baseline collateral score, the score will be converted to baseline collateral status. Baseline collaterals dichotomization will use the following conversion approach:

Dichotomization A (main): where a baseline collateral score of 0-2 indicates Baseline collateral status = Absent, and a baseline collateral score of 3-5 indicates Baseline collateral status = Present

Dichotomization B: where a baseline collateral score of 0 indicates Baseline collateral status = Absent, and a baseline collateral score of 1-5 indicates Baseline collateral status = Present.

Dichotomization C: where a baseline collateral score of 0-1 indicates Baseline collateral status = Absent, and a baseline collateral score of 2-5 indicates Baseline collateral status = Present.

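### SAP Appendix D groups the Barthel biomarker curves by EQ-5D-5L tertiles, so that figure would duplicate the EQ-5D-5L one; relating only Day 90 blood to outcome also leaves out patients who die before that sample

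*SAP*

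**What the plan says.** SAP Appendix D offers exploratory displays of each biomarker against mRS, NIHSS, BI and EQ-5D-5L.

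- **ePDF groups.** The curves are to be drawn for subsets defined by cut points of the Day 90 clinical outcomes. For BI (item c) the rule is "BI: The tertiles of the Day 90 total EQ-5D-5L score would be determined". For EQ-5D-5L (item d) it is "EQ-5D-5L: The tertiles of the Day 90 total EQ-5D-5L score would be determined".
- **Biomarker day.** For the plots, "scatterplots may be generated for each biomarker at Day 90 (horizontal axis) and each clinical outcome at Day 90". For the curves, "the empirical probability distribution function (ePDF) of each biomarker at Day 90 may be displayed graphically". The Spearman coefficients name no day, but they may be shown "either superimposed on the corresponding scatterplots as defined above, or tabulated in a separate table".
- **Early samples.** Protocol 8.1.4 and 8.1.5 schedule blood on Day 1, Day 2 and Day 90. In Appendix D the first two days appear only in the descriptive tables by treatment arm and time.
- **Deaths.** SAP 3.1.7 states: "Subjects who die during the study will be scored as follows for all scheduled visits following the death". The values are mRS 6, NIHSS 42 and BI 0. No EQ-5D-5L value is given.
- **Status.** SAP 3.4.5 puts the statistical treatment of biomarkers outside the Clinical Study Report, and Appendix D is worded throughout as what may be done.

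**The concern.** Item c is a complete analysis rule, and following it gives a figure that does not match its label. A programmer working from the SAP would produce the EQ-5D-5L figure twice, once under a Barthel title. A reader would then take curves sorted by quality of life as curves sorted by independence in daily activities. The SAP declares itself the governing document (sections 1 and 6.4), and the protocol has no biomarker-outcome analysis to fall back on.

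The second matter is one of coverage. The mRS 3-6 group and the NIHSS group of 14 or more include deaths by definition, yet a patient who died before the Day 90 draw has no biomarker value to plot. The displays then describe patients alive and sampled at Day 90. They do not show whether a marker measured during or just after the infusion tracks the later outcome, although the samples for that are already scheduled.

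**Working it through.** **Step 1: items c and d side by side.**

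| Element | Item c (BI) | Item d (EQ-5D-5L) |
|---|---|---|
| Biomarker day | Day 90 | Day 90 |
| Grouping variable | Day 90 total EQ-5D-5L score | Day 90 total EQ-5D-5L score |
| Groups | Tertiles, three curves | Tertiles, three curves |

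Every element agrees, so the figures can differ only in their label. Appendix D contains no BI cut point. Elsewhere the SAP does have one: section 3.4.2(5) compares "subjects achieving functional independence (Barthel Index score ≥ 95 as compared to < 95".

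**Step 2: the score named in item d.** SAP 2.3.2(6) defines a five-digit profile, a single-number index score and the EQ-VAS. It defines no total. The index score is the natural reading, but the item should say so.

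**Step 3: which displays use which sample.**

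| Display | Biomarker day | BI included? |
|---|---|---|
| Scatterplots | Day 90, stated | Yes |
| Spearman coefficients | Day 90, inferred from the link to the scatterplots | Yes |
| ePDF curves | Day 90, stated | No, because of item c |
| Descriptive tables by arm | Days 1, 2 and 90 | Not related to outcome |

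No rule carries an earlier biomarker value forward. A patient who dies before the Day 90 sample is therefore missing from the scatterplots and ePDFs and, on the inferred reading, from the coefficients. Correcting item c does not change this: such a patient has BI 0 but still no Day 90 biomarker.

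**Step 4: how many patients.** The plan states no figure to reproduce, because SAP 2.2.4 reports no power analysis. Inputs are the target of 100 and the attrition figure of 10% for stroke deaths not attributed to treatment, both from SAP 2.2.4.

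- Expected deaths = N × death rate = 100 × 0.10 = 10, or 10 / 3 = 3.3 per arm.
- Binomial probability of at least 5 deaths among 100 at 10%: 0.976.
- Over an assumed range of 5% to 20%: 100 × 0.05 = 5 to 100 × 0.20 = 20 deaths.
- If the biomarker subset is a fraction c of those enrolled and has the same death rate, the count is 10 × c. The documents do not give c, so 10 is an upper limit at that rate.

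Protocol 2.1.2 says about half of EVT patients stay dependent or die. On all 100 enrolled, deaths would then be 10 / 50 = 20% of the mRS 3-6 group, or 5 / 50 = 10% to 20 / 50 = 40% over the assumed range.

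**Step 5: illustration only.** For an early biomarker, with N = 100, 2,000 simulated runs, a bivariate normal model and the worst 10% of outcomes taken as deaths, the mean Spearman coefficient was as follows.

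| Assumed correlation | Deaths scored worst | Deaths dropped |
|---|---|---|
| 0.3 | 0.287 | 0.247 |
| 0.5 | 0.476 | 0.419 |

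This shows the direction of effect when deaths are left out of an early-biomarker analysis. It says nothing about the size of any effect on a Day 90 biomarker.

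**The case against.** The strongest reply is that item c is an obvious slip. It is labelled BI, the lead-in promises cut points of the clinical outcomes, and any programmer would ask. The analyses are optional and even the list of biomarkers is still to come. Relating Day 90 blood to Day 90 outcome is a legitimate cross-sectional question, in which a patient who has died has no place. Most of this stands. It sets the weight of the point and makes the early-sample displays an improvement, not the correction of an error. It does not make item c right: as written, the rule yields a mislabelled duplicate.

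Several stronger readings are tempting, and the documents do not support them:

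- **That the biomarker-Barthel relation goes unexamined.** BI is listed in the scatterplots and covered by the Spearman coefficients. Only the ePDF display is lost.
- **That deaths vanish from every display.** The day for the Spearman coefficients is inferred. The Day 90 visit may also take place up to 21 days early (Protocol Table 1-1), so a patient sampled then who dies later keeps a biomarker value.
- **That patients seen remotely have no Day 90 blood.** Protocol Table 1-1 allows remote contact but does not say that no sample is obtained. This is a reasonable inference, not a stated fact.
- **That 20% to 40% of the poor-outcome group is lost.** These shares refer to everyone enrolled. RNA sampling needs separate optional consent, and plasma sampling depends on the site. The 10% is an attrition figure for stroke deaths, not all-cause mortality, and anything above 20% rests on assumed mortality.

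**Conclusion.** Item c is wrong as written and needs a one-line correction; this follows from the text alone. Item d should name a score that the SAP defines. The restriction to Day 90 biomarkers is a defensible choice with a known gap, and it can be supplemented cheaply.

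The size of that gap is illustrative: about 10 of 100 patients, assuming the SAP's stroke-death figure, full enrolment, sampling of every patient, and deaths that come before the Day 90 draw. The number in the consenting subset will be smaller and cannot be derived from the documents. The priority is low, because nothing here bears on a primary or secondary endpoint or on the safety conclusions.

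**What to change.** 1. **Item c:** replace the EQ-5D-5L score with the Day 90 BI score. Keeping tertiles is the smallest change and preserves three curves, but BI moves in steps of 5 (SAP Table 4), so a rule for ties at the boundaries is needed. The cut at 95 from SAP 3.4.2(5) avoids that and gives two curves.
2. **Item d:** name the EQ-5D-5L index score of SAP 2.3.2(6).
3. **Early samples:** add scatterplots, Spearman coefficients and ePDFs of the Day 1 and Day 2 biomarkers against Day 90 mRS, NIHSS and BI. State the biomarker day for every coefficient. This restores deaths that occur after an early draw in a consenting patient.
4. **Labels:** mark the Day 90 biomarker displays as limited to patients sampled at Day 90. Note that deaths stay absent from the EQ-5D-5L displays, early samples included, because the SAP assigns them no value.

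The cost is a wording change and a few more exploratory plots from blood already scheduled. It can be made in a SAP addendum, or alongside the biomarker list that Appendix D says may follow.
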